5.5.4.1 Administration

Secukinumab Solution for Subcutaneous Injection (active or placebo, respectively) will be provided in prefilled syringes (PFS).

Single syringes will be packed in individual boxes. The boxes containing the safety prefilled syringes with study treatment solution should be kept at 2 to 8°C (36°F and 46°F) and protected from light. Prior to administration the boxes containing the safety prefilled syringes with study treatment solution should be allowed to come to room temperature unopened for about 20 minutes before administration. Used safety syringe should be disposed immediately after use in a sharps container.

Patients will be instructed at baseline by the site staff on how to self-inject either secukinumab or placebo (blinded) via PFS following the IFU. After the Baseline Visit, the injections will be self-administered into the appropriate site of the body (thighs, arms, abdomen), and each injection should be given at a different injection site. Each new injection should be given at least one inch from the previously used site. If subject chooses the abdomen, 2 inches area around navel should be avoided. Investigational drug should not be injected into areas where the skin is tender, bruised, red, or hard, or where subject has scars or stretch marks. Injection sites should be changed to reduce the risk of reaction.

All study treatment will be self-administered subcutaneously after visit study assessments have been completed. While patients are encouraged to self-inject, continued assistance by the site or home nurse is acceptable.

5.5.5 Permitted dose adjustments and interruptions of study treatment

Study treatment dose adjustments are not permitted.

Study treatment interruptions are not permitted with the following exceptions:

- If, in the opinion of the investigator, a subject is deemed to be placed at a significant safety risk unless dosing is temporarily interrupted. In such cases study treatment should be interrupted only during the time that this risk is present and ongoing. Study treatment can be restarted at the next scheduled visit after resolution of the safety risk.
- The effect of secukinumab on live vaccines is unknown; therefore live vaccines should not be administered during participation in the study. In case a live vaccine has been administered due to a medical urgency, the subject **must** be discontinued from study treatment as per [Section 5.6.2](#). Non-live vaccinations are permitted during the study.

Study treatment interruptions must be recorded on the corresponding Dosage Administration Record eCRF page and all assessments should be completed as scheduled.

5.5.6 Rescue medication

Rescue medication is not permitted during the study. Patients will be free to discontinue participation in the study at any time.

5.5.7 Concomitant medication

Patients should be instructed to notify the study site about any new medications he/she takes after being enrolled into the study. All medications, procedures and significant non-drug therapies (including physical therapy and blood transfusions) administered after the patient was enrolled into the study must be recorded in the appropriate eCRF.

Guidelines for the use of specific medications are provided below:

Methotrexate (MTX)

Patients taking MTX (up to 25 mg/week) must be on a stable dose for at least 4 weeks before the Baseline Visit and maintained stable throughout the duration of the study.

Folic acid

Patients on MTX must be taking folic acid supplementation before the Baseline Visit and during the study to minimize the likelihood of MTX associated toxicity.

Sulfasalazine

Subjects taking sulfasalazine (≤ 3 g/day) must be on a stable dose for at least 4 weeks before the Baseline Visit and maintained stable throughout the duration of the study.

Leflunomide

Subjects taking leflunomide (≤ 20 mg/day) must be on a stable dose for at least 4 weeks before the Baseline Visit and maintained stable throughout the duration of the study.

Low Strength opioids

Subjects are allowed to take low strength opioids PRN. However, patients should not take a dose of low strength opioids within 24 hours of a study visit. High potency opioid analgesics (e.g., methadone, hydromorphone, morphine) are prohibited in this study.

Systemic corticosteroids

Treatment with systemic corticosteroids is permitted up to a maximum daily dosage of 10 mg prednisone equivalent and the dose is stable within the 2 weeks preceding the Baseline Visit. The subject should remain on a stable dose throughout the duration of the study.

Higher-dose, time-limited corticosteroid courses (bursts) may be permitted for exacerbations of medical conditions unrelated to AS (e.g., asthma, chronic obstructive pulmonary disease (COPD), contact dermatitis) after baseline. Any change in the dose of systemic corticosteroids during the trial must be recorded on the corresponding CRF.

[figure not shown]
Intra-articular corticosteroids are not permitted within the 4 weeks preceding the Baseline Visit and up to Week 52.

Non-steroidal anti-inflammatory drugs (NSAIDs) (including COX-1 or COX-2 inhibitors) and acetaminophen

Patients on regular use of NSAIDs or acetaminophen should be on stable dose for at least 2 weeks before the Baseline Visit to allow inclusion in the study. They should remain on stable dose in the study up to Week 52.

Subjects taking NSAIDs or acetaminophen PRN within the 2 weeks before baseline can continue to do so in the study; however, they have to refrain from any intake during the 24 hours before a visit.

Any change of the NSAIDs or acetaminophen treatment during the trial should be recorded on the corresponding eCRF page

5.5.9 Emergency breaking of assigned treatment code

Emergency treatment code breaks should only be undertaken when it is essential to treat the patient safely and efficaciously. Most often, study treatment discontinuation and knowledge of the possible treatment assignments are sufficient to treat a study patient who presents with an emergency condition. Emergency treatment code breaks are performed using the IRT system. When the Investigator contacts the IRT system to break a treatment code for a patient, he/she must provide the requested patient identifying information and confirm the necessity to break the treatment code for the patient. The Investigator will then receive details of the investigational drug treatment for the specified patient and a confirmation via email and/or fax. The system will automatically inform the Novartis monitor for the site and the Clinical Trial Lead (CTL) that the code has been broken.

It is the Investigator's responsibility to ensure that there is a procedure in place in case of an emergency. The Investigator will inform the patient how to contact his/her backup in cases of emergency when he/she is unavailable. The Investigator will provide protocol number, study treatment name if available, patient number, and instructions for contacting Novartis Country Pharma Organization CPO (or any entity to which it has delegated responsibility for emergency code breaks) to the patient in case an emergency treatment code break is required at a time when the Investigator and backup are unavailable.

5.6 Study completion and discontinuation

5.6.1 Study completion and post-study treatment

The last scheduled administration of therapy will be at Visit 18/Week 48. A subject's study participation is completed once Visit 19/Week 52 has been completed. After this date, any SAEs that occur in the following 30 days must be reported. The investigator will also follow any AEs for which there is no outcome that can be reported at the final study visit. Pregnancies will be followed until the outcome of the pregnancy is known.

Information on the subject's completion or discontinuation of the study and the reason for discontinuation of the study will be recorded on the corresponding CRFs.

In any case, the investigator or site staff must contact the IRT system as soon as possible to record the subject's study completion (Week 52) and/or withdrawal from the trial.

The study as a whole will be completed once all enrolled patients have completed the study per the protocol and the clinical database has been locked. Recruitment into the study will be terminated by the sponsor once the targeted number of randomized patients has been met or is foreseen to be met with the patients already in screening. Patients who have been screened and have a screening visit recorded in the IRT system at the time that the planned enrollment number is met will be allowed to enter the trial and to be randomized if they are eligible.

Upon completion of study participation, patients will return to individual medical treatment, as determined by their treating physician.

The Investigator must provide follow-up medical care for all patients who are prematurely withdrawn from the study, or must refer them for appropriate ongoing care.

5.6.2 Discontinuation of study treatment

Discontinuation of study treatment for a subject occurs when study drug is stopped earlier than the protocol planned duration, and can be initiated by either the subject or the investigator.

Study treatment must be discontinued if the investigator determines that continuation of study treatment would result in a significant safety risk for a subject. **Patients that discontinue study treatment cannot continue in the trial. They must be discontinued from the trial altogether.**

The following circumstances **require** study treatment discontinuation and consequently discontinuation from the trial:

- Withdrawal of informed consent
- Emergence of the following adverse events:
 - a. Any severe or serious adverse event that in the judgment of the investigator/qualified site staff, taking into account the subject's overall status, prevent the subject from continuing study treatment;
 - b. Any laboratory abnormalities that in the judgment of the investigator are clinically significant and are deemed to place the subject at a safety risk for continuation in the study (A general guidance on clinically notable laboratory values is provided in [REDACTED]).

c. Life-threatening infection

- Pregnancy;

- Emergency unblinding
- Patient refusal to complete PRO questionnaires at Baseline, Week 12 or Week 16
- Any other protocol deviation that results in a significant risk to the subject's safety;

For any subject whose treatment code has been broken inadvertently for any reason, the appropriate personnel from the site and Novartis will assess whether study treatment should be discontinued.

The investigator must also contact the IRT system to register the subject's discontinuation from study treatment.

Patients may voluntarily withdraw from the study for any reason at any time. They may be considered withdrawn if they state an intention to withdraw, fail to return for visits, or become lost to follow-up for any other reason.

5.6.3 Withdrawal of informed consent

Patients may voluntarily withdraw consent to participate in the study for any reason at any time.

Withdrawal of consent occurs only when a patient does not want to participate in the study anymore, and does not want any further visits or assessments, and does not want any further study-related contacts.

If premature withdrawal occurs for any reason, the investigator must make every effort (e.g. telephone, e-mail, letter) to determine the primary reason for this decision and record this information in the patient source and on the appropriate study completion eCRF.

Patients who withdraw consent should return for an End of Study Visit (see [Table 6-1](#)). The End of Study Visit should be scheduled approximately four weeks after the last study treatment, and should be performed before any new treatment is initiated. After the End of Study Visit, any SAEs that occur in the following 30 days must be reported. The investigator will also follow any AEs for which there is no outcome that can be reported at the final study visit. Pregnancies will be followed until the outcome of the pregnancy is known.

Patients who are prematurely withdrawn from the study will not be replaced by newly enrolled patients.

5.6.4 Loss to follow-up

For patients who are lost to follow-up (i.e., those patients whose status is unclear because they fail to appear for study visits without stating an intention to withdraw), the investigator should show "due diligence" by documenting in the source documents steps taken to contact the subject, e.g. dates of telephone calls, registered letters, etc.

5.6.5 Early study termination by the sponsor

The study can be terminated by Novartis at any time for any reason. This may include reasons related to the benefit risk assessment of participating in the study, practical reasons, or for regulatory or medical reasons (including slow enrollment). Should this be necessary, the subject should be seen as soon as possible and treated as a prematurely withdrawn as described in [Section 5.6.2](#). The investigator may be informed of additional procedures to be followed in order to ensure that adequate consideration is given to the protection of the subject's interests. The investigator will be responsible for informing Institutional Review Board/Independent Ethics Committee (IRBs/ECs) of the early termination of the trial.

6 Visit schedule and assessments

[Table 6-1](#) lists all of the assessments and indicates with an "X" when the visits are performed. Assessments that will only be reported in the source documentation are marked with an 'S'.

Patients/subjects must be seen for all visits on the designated day, or as close to it as possible. Missed or rescheduled visits should not lead to automatic discontinuation. For patients unable to travel to the clinic for their study visit, flexible study visits (home nursing study visits) and telemedicine/telephone visits with direct to patient shipment of study drug are alternative options for all post-Baseline study visits. For more information regarding flexible study visits, please refer to the Site Manual for Home Visits (Flexible Study Visits). Patients who prematurely discontinue the study for any reason should be scheduled for an End of Study Visit as soon as possible, at which time all of the assessments listed will be performed. At this End of Study Visit, all dispensed investigational product should be reconciled and the adverse event and concomitant medications reconciled on the CRF.

If patients do not have a chest X-ray available within 3 months of screening, the X-ray should be performed only after it is certain the subject meets inclusion/exclusion criteria in order to minimize unnecessary exposure to radiation.

Patients evaluated at Screening Visit 1 and 2 for Inclusion/Exclusion criteria should not be screen failed on the basis of a medication requiring washout, unless the subject will be unable to complete the washout in the appropriate time frame before the Baseline Visit.

Screening will be flexible in duration based on the time required to be evaluated for eligibility. Sufficient time is allowed for potential medication washout, in addition to all other assessments indicated in [Table 6-1](#). Upon the completion of screening and confirmation that all inclusion and none of the exclusion criteria have been met, the subject may begin the Baseline Visit.

Screening will consist of two consecutive visits. During Screening Visit 1 (SV1) and Screening Visit 2 (SV2), initial assessments will be performed as outlined in [Table 6-1](#).

Patients who may be eligible for Screening Visit 2 immediately following Screening Visit 1 should have at least one week in between these two screening visits.

Premature Discontinuation

For patients who discontinue study treatment prematurely for any reason after baseline, an End of Study Visit must be performed approximately four weeks after the last dose of study treatment. In accordance with SAE reporting guidelines, any SAEs reported in the 30 days after the End of Study Visit, regardless of causality, must be reported to Novartis within 24 hours of learning of its occurrence and recorded in the eCRF.

Documentation of attempts to contact the subject should be recorded in the source documentation.

Unscheduled visits

Patients may be seen at any time for an unscheduled visit, e.g., if they experience deterioration or AEs that in the opinion of the investigator/qualified site staff need intervention or repeat laboratory testing. The assessment(s) performed at an unscheduled visit must include at minimum: an assessment of concomitant medication and procedures/significant non-drug therapies, vital signs, and an AE/SAE assessment. Any additional assessments performed are at the investigator/qualified site staff's discretion. During an unscheduled visit, study treatment will not be administered.

Table 6-1 Assessment schedule

Period	SCR ¹		Treatment Period 1 (Open-Label)								Treatment Period 2 (Double-Blind or Open-Label)								Telemedicine/ telephone visit	Unscheduled	Notes		
	-13 to -3	-2 to BL	BL	1	2	3	4	8	12	16	20	24	28	32	36	40	44	48				52/Study Completion/ EOS ²	
Visit No	1	2	3	4	5	6	7	8	9	10	11	12	13	14	15	16	17	18	19				
Assessments																							
Obtain informed consent	X																						See section 10.2
Inclusion / exclusion criteria	X	X	X																				See sections 4.1 – 4.2
Demographics	X																						See section 6.3
General Medical history / previous therapies	X																						See section 6.3
Relevant AS medical history / current medical conditions	X																						See section 6.3
Washout evaluation / instruction	S																						See Table 5-1
Modified NY criteria	S	S	S																				See section 13.2
Radiologic evidence (x-ray) to central reader		X																					See section 6.6.9

Period	SCR ¹		Treatment Period 1 (Open-Label)								Treatment Period 2 (Double-Blind or Open-Label)								Telemedicine/ telephone visit	Unscheduled	Notes		
	Week	-13 to -3	-2 to BL	BL	1	2	3	4	8	12	16	20	24	28	32	36	40	44				48	52/Study Completion/ EOS ²
Visit No	1	2	3	4	5	6	7	8	9	10	11	12	13	14	15	16	17	18	19				
Assessments																							
Smoking and alcohol history			X																				See section 6.3
Cardiovascular medical history	X																						See section 6.3
Physical Exam ³		S	S				S	S	S	S	S	S	S	S	S	S	S	S	S				See section 6.6.4
Weight		X	X							X													See section 6.6.6
Height		X																					See section 6.6.6
Vital signs		X	X	X	X	X	X	X	X	X	X	X	X	X	X	X	X	X	X	X		X	See section 6.6.5
Chest X-ray		X																					See section 6.6.2
ECG		X																					See section 6.6.3
Prior/ Concomitant medication/ non-drug therapy	X	X	X	X	X	X	X	X	X	X	X	X	X	X	X	X	X	X	X	X	X	X	See section 5.5.7

Period	SCR ¹		Treatment Period 1 (Open-Label)								Treatment Period 2 (Double-Blind or Open-Label)												
Week	-13 to -3	-2 to BL	BL	1	2	3	4	8	12	16	20	24	28	32	36	40	44	48	52/Study Completion/ EOS ²	Telemedicine/ telephone visit	Unscheduled	Notes	
Visit No	1	2	3	4	5	6	7	8	9	10	11	12	13	14	15	16	17	18	19				
Assessments																							
IRT transaction	S	S	S	S	S	S	S	S	S	S	S	S	S	S	S	S	S	S	S	S	X		See section 5.3
Administration of s.c. study treatment via PFS			X	X	X	X	X	X	X	X	X	X	X	X	X	X	X	X	X		X		See section 5.5.4
Adverse Events/SAEs (inc. injection site reaction & occurrence of infections)	X	X	X	X	X	X	X	X	X	X	X	X	X	X	X	X	X	X	X	X	X	X	See section 7.1 – 7.2
QuantiFERON TB-Gold test		X																					See section 6.6.1
Hematology, blood chemistry ⁴		X	X						X	X			X			X				X			See section 6.6.7.1 - 6.6.7.2
Serum pregnancy test		X																					See section 6.6.8
Urinalysis/Urine pregnancy test			X				X		X	X		X		X		X				X			See section 6.6.7.3 and 6.6.8
HLA-B27		X																					See section 6.6.7.4

Period	SCR ¹		Treatment Period 1 (Open-Label)								Treatment Period 2 (Double-Blind or Open-Label)								Telemedicine/ telephone visit	Unscheduled	Notes	
	Week	-13 to -3	-2 to BL	BL	1	2	3	4	8	12	16	20	24	28	32	36	40	44				48
Visit No	1	2	3	4	5	6	7	8	9	10	11	12	13	14	15	16	17	18	19			
Assessments																						
Responder status assessment										X										X	See section 3.1	
BASDAI	X ⁵	X	X	X	X	X	X	X	X	X	X	X	X	X	X	X	X	X	X	X	X	See section 6.5.2.7
Patient's global assessment of disease activity	X ⁵	X	X	X	X	X	X	X	X	X	X	X	X	X	X	X	X	X	X	X	X	See section 6.5.2.4
ASAS-HI			X				X	X	X	X	X	X	X	X	X	X	X	X	X	X	X	See section 6.5.4
FACIT-Fatigue v4			X	X	X	X	X	X	X	X	X	X	X	X	X	X	X	X	X	X	X	See section 6.5.6

Period	SCR ¹		Treatment Period 1 (Open-Label)								Treatment Period 2 (Double-Blind or Open-Label)											
Week	-13 to -3	-2 to BL	BL	1	2	3	4	8	12	16	20	24	28	32	36	40	44	48	52/Study Completion/ EOS ²	Telemedicine/ telephone visit	Unscheduled	Notes
Visit No	1	2	3	4	5	6	7	8	9	10	11	12	13	14	15	16	17	18	19			
Assessments																						
Treatment period 1 completion form										X										X		
Treatment period 2 completion form																			X	X		

² Patients who discontinue prematurely or withdraw consent should return for an End of Study Visit. The End of Study Visit should be scheduled approximately four (4) weeks after the last study treatment and should be performed before any new treatment is initiated.

³ The Physical Exam is documented in the source; not in the database. If flexible study visits are permitted, a limited physical assessment will be performed by the home nurse in place of a complete physical examination.

⁴ Fasting sample

⁵ Measures captured only for TNF inhibitor inadequate responders currently on a TNF inhibitor and prior to discontinuation/washout.

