- b. **Inadequate responders** will enter Treatment Period 2 and will be randomized (1:1, double-blinded) to secukinumab 300 mg or secukinumab 150 mg very 4 weeks through Week 48. Subjects will know that they are on secukinumab, but will be blinded to dose, as they will not know whether they are receiving 150 mg or 300 mg.
- c. **Nonresponders** will be discontinued from the study at Week 16.

The only condition that will be placed on enrollment targets is that no less than 60% of patients (162 patients) are TNF α inhibitor naive (or, no more than 40% of patients are TNF-IR). In theory the percentage of TNF α inhibitor naive patients could reach 100%, although that is not anticipated.

Patients may discontinue the study at any time. If rescue treatment with prohibited medications occurs, patients will be discontinued from the study and should return for an End of Study Visit (see Table 6-1). The End of Study Visit should be scheduled approximately four weeks after the last study treatment, and should be performed before any new treatment is initiated. After the End of Study Visit, any SAEs that occur in the following 30 days must be reported.

Figure 3-1 Study design

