7.2.1.1 SAE Reporting

To ensure patient safety, every SAE, regardless of causality, occurring after the patient has provided informed consent and until 30 days following the last study visit must be reported to Novartis within 24 hours of learning of its occurrence.

Any SAEs experienced after the 30 day period following the last study visit should only be reported to Novartis safety if the investigator suspects a causal relationship to study treatment.

All follow-up information for the SAE including information on complications, progression of the initial SAE and recurrent episodes must be reported as follow-up to the original episode within 24 hours of the investigator receiving the follow-up information. An SAE occurring at a different time interval or otherwise considered completely unrelated to a previously reported one must be reported separately as a new event.

Information about all SAEs is collected and recorded on the Serious Adverse Event Report Form; all applicable sections of the form must be completed in order to provide a clinically thorough report. The investigator must assess the relationship of each SAE to each specific component of study treatment, (if study treatment consists of several components) complete the SAE Report Form in English, and submit the completed form within 24 hours to Novartis. Detailed instructions regarding the submission process and requirements for signature are to be found in the investigator folder provided to each site.

Follow-up information is submitted as instructed in the investigator folder. Each re-occurrence, complication, or progression of the original event must be reported as a follow-up to that event regardless of when it occurs. The follow-up information should describe whether the event has

resolved or continues, if and how it was treated, whether the blind was broken or not, and whether the patient continued or withdrew from study participation.

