- b. **Inadequate responders** will enter Treatment Period 2 and will be randomized (1:1, double-blinded) to secukinumab 300 mg or secukinumab 150 mg very 4 weeks through Week 48. Subjects will know that they are on secukinumab, but will be blinded to dose, as they will not know whether they are receiving 150 mg or 300 mg.
- c. **Nonresponders** will be discontinued from the study at Week 16.

The only condition that will be placed on enrollment targets is that no less than 60% of patients (162 patients) are TNF $\alpha$  inhibitor naive (or, no more than 40% of patients are TNF-IR). In theory the percentage of TNF $\alpha$  inhibitor naive patients could reach 100%, although that is not anticipated.

Patients may discontinue the study at any time. If rescue treatment with prohibited medications occurs, patients will be discontinued from the study and will return for an End of Study Visit. The End of Study Visit will be scheduled approximately four weeks after the last study treatment, and will be performed before any new treatment is initiated. After the End of Study Visit, any SAEs that occur in the following 30 days will be reported.

[figure not shown]

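### The opening of Protocol Section 6 calls early leavers to a prompt End of Study Visit, against the four-week rule elsewhere; following it can end all-causality SAE reporting up to 28 days sooner

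*Protocol*

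**What the plan says.** The opening text of Protocol Section 6 covers every patient who leaves the study prematurely, whatever the reason. Such patients "should be scheduled for an End of Study Visit as soon as possible, at which time all of the assessments listed will be performed".

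Other places time the same visit from the last dose:

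- **Protocol Section 6, Premature Discontinuation**, for anyone who stops study treatment after baseline, for any reason: "an End of Study Visit must be performed approximately four weeks after the last dose of study treatment".
- **Protocol Table 6-1, footnote 2**, for premature discontinuation and withdrawal of consent: "scheduled approximately four (4) weeks after the last study treatment and should be performed before any new treatment is initiated".
- **Protocol 3.1**, next to the text on rescue with prohibited medication: "scheduled approximately four weeks after the last study treatment, and should be performed before any new treatment is initiated".
- **Protocol 5.6.3**, for withdrawal of consent: "The End of Study Visit should be scheduled approximately four weeks after the last study treatment".
- **SAP 1.1**, following Protocol 3.1: the visit "will be scheduled approximately four weeks after the last study treatment, and will be performed before any new treatment is initiated".

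Two further provisions matter. Protocol 5.6.2 states: "Patients that discontinue study treatment cannot continue in the trial". Protocol 7.2.1.1 requires that every SAE, whatever its cause, from consent "until 30 days following the last study visit must be reported to Novartis within 24 hours". After that, an SAE is reportable only if the investigator suspects that study treatment caused it.

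**The concern.** The first half of Section 6 tells a site to see an early leaver promptly. The second half tells it to wait until about four weeks after the last dose. The two cannot be assigned to different patients by separating leaving the study from stopping treatment, because 5.6.2 makes anyone who stops treatment leave the trial.

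The visit date matters because it starts the 30-day clock for all-causality SAE reporting. A site that follows the opening sentence can close that window earlier than another site would for the same patient. SAEs not thought to be related could then be collected over different lengths of follow-up, depending on which paragraph the site read.

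**Working it through.** The documents state no figure for this point, so there is none to reproduce.

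**Inputs**

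- Four-week rule: visit at about day 28 after the last dose (places listed above).
- All-causality SAE reporting ends 30 days after the last study visit (7.2.1.1).
- Last dose at Week 48 and last visit at Week 52 for completers (5.6.1).
- d = days from last dose to the End of Study Visit under the opening sentence. The documents give no distribution of d, so the values below are assumed.
- n = day on which new treatment has to start. Protocol 3.1, 5.6.3 and footnote 2 put the visit before any new treatment, so n < 28 can bring it forward.

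**Reference case, completers.** (52 − 48) × 7 = 28 days from last dose to last visit; 28 + 30 = day 58. The four-week rule gives early leavers about the same reporting window.

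**Formulae**

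- Four-week rule: reporting ends on about day min(28, n) + 30, or day 58 if no new treatment is needed before day 28.
- Opening sentence: reporting ends on day d + 30.
- Days lost: max(0, min(28, n) − d).

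**No new treatment before day 28**

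| d | Reporting ends, opening sentence | Reporting ends, four-week rule | Days lost |
|---|---|---|---|
| 0 | 30 | 58 | 28 |
| 7 | 37 | 58 | 21 |
| 14 | 44 | 58 | 14 |
| 21 | 51 | 58 | 7 |
| 28 | 58 | 58 | 0 |

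At d = 35 four weeks have already passed. Reporting ends on day 65 and nothing is lost.

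**New treatment needed on day 10.** The four-week text itself ends reporting by 10 + 30 = day 40. With d = 7, reporting ends on day 37 and 3 days are lost; with d = 10, none.

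**Who could be affected, on the planned numbers (9.8)**

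- Treatment Period 1 leavers: 0.10 × 270 = 27, some of whom may be affected.
- Week 16 non-responders: 270 − 27 = 243, and 0.10 × 243 = 24.3, about 24. Their last dose is at Week 12 (5.2), so d = (16 − 12) × 7 = 28 and the loss is 0.
- Anyone who stops at a 4-weekly visit before being dosed likewise has d = 28 and loses nothing.
- Treatment Period 2: no dropout figure is given, so no count can be made.

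**The case against.** The strongest reply is that Section 6 settles the matter itself. A specific paragraph with a firm obligation normally overrides a general introductory sentence, and footnote 2 repeats four weeks beside the schedule that sites work from. On that view the opening sentence means only that the appointment should be booked promptly. The first part stands: a careful reader would conclude that four weeks prevails. The booking reading does not stand, because the sentence goes on to say that all listed assessments are done at that time, which ties the timing to the visit.

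Other points stand in part:

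- Protocol 3.1, 5.6.3 and SAP 1.1 state the rule for rescue or consent withdrawal, so only the Premature Discontinuation paragraph and footnote 2 cover early leavers in general. Those two are enough for a direct conflict.
- A site that sees the patient early and again at four weeks loses nothing, since the later visit is then the last one. No text asks for two such visits, but a site could hold both.
- The full 28 days needs dosing, departure and the complete visit on one day. It is an upper bound.
- The 27 Treatment Period 1 leavers may include patients lost to follow-up who never have the visit, so 27 is a loose ceiling.
- The requirement to hold the visit before new treatment could mean that treatment waits. The term n then drops out and the loss is max(0, 28 − d), with the same maximum.
- The practical effect is small, as set out in the verdict.

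**Conclusion.** The concern holds, as a minor inconsistency. The Section 6 opening gives an operative instruction that conflicts with the protocol's own mandatory rule for the same patients. A site that follows it, and holds no later visit, shortens all-causality SAE reporting by 0 to 28 days per early leaver. The size depends on d, which is assumed over its range, and on whether new treatment has to start before day 28.

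The reach is limited. Suspected SAEs stay reportable after the 30 days (7.2.1.1), and adverse events already detected are followed until they resolve or are judged permanent (7.1). The primary endpoint is unaffected, because early leavers count as nonresponders from discontinuation (SAP 2.5.3). The exposure and treatment-emergent windows of last dose + 84 days (SAP 2.4.1 and 2.8.1) do not move. What can differ between sites is how long unrelated SAEs are reported within those windows.

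**What to change.** In the opening sentence of Protocol Section 6 only, replace the timing phrase with: *about four weeks after the last dose of study treatment; before any new treatment, if that has to start sooner; without delay, if four weeks have already gone by*. Leave the prompt visit in 5.6.5 as it is. It applies to termination by the sponsor, where an early visit for every patient can be intended and does not make sites differ.

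The SAP history contains an entry dated 08-Jul-2021, after database lock, and Protocol 5.4 puts the lock after all Week 52 visits. The wording change is therefore useful now only where this text is reused. The step still open for this study is in the report: describe the interval from last dose to End of Study Visit for early leavers and give the number seen before day 28.

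The cost is one phrase in one sentence, and one descriptive line from dosing and visit dates already collected.
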